7.2.1.3 Treatment-emergent adverse events related to study treatment

TEAEs related to study drug are those TEAEs which are reported as related to study treatment by the investigator.

7.2.1.4 Treatment-emergent adverse events by intensity

AE intensity is reported by the investigator using the following severity scale: mild, moderate, or severe.

For AEs with multiple intensities reported, the worst reported severity will be considered.

7.2.1.5 Serious adverse events

A serious AE (SAE) is an AE that has been reported as serious by the investigator in the CRF.

7.2.1.6 Adverse events leading to death

An AE will be considered as leading to death if the AE outcome is fatal.

7.2.1.7 Adverse events leading to study treatment discontinuation

Not applicable.

7.2.1.8 Other adverse event categories

Two AEs of special interest (AESIs) are defined, one will include any AE included in MedDRA SMQ "Haemorrhage (excl. lab)" of narrow terms, the other will include any AE included in the MedDRA high level group term "Administration site reaction"

AESIs will be summarized and listed.

7.2.2 Analysis

For all the AE variables described in Section 7.2.1, the incidence of subjects with TEAEs will be summarized (frequency counts and percentages) by SOC and/or PT.

For TEAEs by intensity, the incidence of subjects with events will be summarized (frequency counts and percentages) by SOC and/or PT and by maximum intensity (worst).

All AEs will be listed separately for subjects included in the SAF and for subjects not included in the SAF. SAEs will be flagged.

Listings will also be provided for SAEs and AESIs for the SAF only.

7.2.3 Analyses for key study data disclosure to regulatory authorities

The analyses described in Section 7.2.2 will also be performed on number of event occurrences, i.e., summarizing the total number of events, for SAEs, treatment-related SAE, and non-serious AEs.

7.3 Death

Death will be considered to have occurred if a primary cause of death is reported in the CRF 'Death' form.

The original terms used by the investigators to describe deaths (i.e., death cause) are assigned PTs for classification and tabulation using the latest implemented MedDRA version dictionary.

Death will be classified as on study deaths (from study start to End-of-Study [EOS]) and treatment-emergent deaths (within 2 days from study drug administration).

All deaths including cause of death will be listed, and flagged as per period of occurrence (screening and treatment periods).

7.4 Laboratory tests

7.4.1 Measurements

Except coagulation test (activated clotting time) performed locally and used for the analysis described in this section, only laboratory data received from the central laboratory [see protocol section 7.2.5.2] will be included in the analyses described in this section.

However, all laboratory data received from local laboratories will be included in the listings.

Treatment-emergent laboratory abnormalities are central laboratory abnormalities for which blood sample collection were collected at time of study drug administration or within the first 48 hours (2 days) after study administration, and that were not present at baseline.

Worst treatment-emergent marked laboratory abnormalities [see [Appendix C](#)] will be summarized by dose group.

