#### 3.1.1 Study periods

The study is conducted during the hospitalization of the subject for AMI and the subjects will remain hospitalized during the entire study duration. The study comprises the following consecutive periods:

[figure not shown]
**Screening period:** Starts when the subject gives informed consent (orally or in writing, as described in Section 1.4.3) and ends with subject's randomization.

**Treatment period:** Starts with subject's randomization and ends after the End-of-Study (EOS) assessments, approximately 48 h after the administration of a single study treatment dose.

The visit schedule and protocol-mandated procedures will be performed according to the table of assessments [Table 2] and are described in Section 7.

The overall study design is depicted in Figure 1.

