### 3.2 Study design rationale

The duration of the treatment period is justified by the primary objective, which is to characterize the onset of IPA after a single s.c. injection of ACT-246475 at two different doses in subjects with AMI.

The choice of the same two doses (i.e., 8 and 16 mg) as in the ongoing ID-076A201 study (see Section 5.1.1 for detailed rationale on dose selection), will provide supportive information for the selection of the dose to be tested in the Phase 3 pivotal study.

The IPA analysis will be performed with the VerifyNow® method. Results from VerifyNow® are well correlated with those obtained with the light transmission aggregometry (LTA) method [Varenhorst 2009, Gremmel 2015]. The VerifyNow® method has been preferred as it is more standardized than the LTA method and it is the method used for primary PD analysis in the ongoing ID-076A201 study in subjects with stable CAD. In addition, the volume of blood required per sample is higher for LTA (6 mL) than for the VerifyNow® method (3 mL). Accordingly, using the VerifyNow®

method will reduce the amount of blood collected for study purposes in a population with acute ischemic event.

The trial is conducted open-label to allow the investigator to adapt the standard AMI treatments to an individual subject's needs (e.g., antiplatelet and anticoagulant treatment). In addition, the primary endpoint being a pharmacological readout (P2Y12 reaction units [PRU] value at 30 min) with no room for data interpretation, the open-label design is fully justified. Because of the limited sample size and the absence of a placebo group, the presentation of the safety data will be purely descriptive.

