### **7.2.3 Pharmacokinetic and pharmacodynamic assessments**

#### **7.2.3.1 Pharmacokinetic assessments**

##### *7.2.3.1.1 Procedures for blood sampling*

Blood will be collected by direct venipuncture or via an i.v. catheter placed in an antecubital vein in the arm in a 4 mL Monovette® or equivalent tubes containing ethylene diamine tetra-acetic acid (EDTA).

PK blood samples have to be processed within 30 min of collection. Instructions regarding sample collection, processing, labeling, and storage conditions are detailed in the laboratory manual.

The time points for PK assessment blood samples are described in [Table 2](#).

The date and exact actual clock time of collection of each blood sample will be entered in the eCRF.

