#### **7.2.3.2 Pharmacodynamic assessments**

##### *7.2.3.2.1 Procedures for blood sampling*

The different time points for PD blood samples collection are detailed in [Table 2](#).

When applicable, the blood samples for PD assessments are to be preferably collected first, followed by blood samples for PK then blood samples for safety assessments. A 2 mL volume of blood needs to be discarded prior to collection of the PD blood samples.

PD blood samples will be collected by direct venipuncture or via an i.v. catheter placed in an antecubital or large forearm vein in the arm, using 18–21 gauge needles.

One blood sample will be drawn into 3 mL vacuum tubes for each VerifyNow® assay. Collection tubes will contain phenylalanine-proline-arginine-chloromethylketone (PPACK) as an anticoagulant. The platelet aggregation assays must be performed within 1 h of blood collection. The date and the exact actual clock time of collection of each blood sample (including the unscheduled ones, if any) will be entered in the eCRF.

Detailed handling instructions for PD samples are provided in the laboratory manual.

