##### **10.2.4.3 Laboratory data**

Laboratory analyses are based on data received from the central laboratory [see Section 7.2.5.2]. All collected laboratory data are taken into account regardless of whether they correspond to scheduled or unscheduled assessments.

*EOS laboratory test* refers to the laboratory test performed at the 48 h post-dose time point.

For each continuous laboratory variable, the following will be summarized:

- Absolute value at each time point,
- Absolute change from baseline to each measured time point,
- Treatment-emergent marked laboratory abnormalities (i.e., samples date/time  $\geq$  date/time of first study treatment administration and  $\leq$  48 h after date/time of last study treatment administration).

For categorical laboratory variables, the proportion of subjects by category at each time point will be summarized.

Unless stated otherwise, no imputation for missing laboratory values will be performed.

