6.8.1.1 Variable

The primary pharmacodynamic (PD) endpoint is the *PD response* that is defined for each subject as a PRU < 100 at 30 min after study drug injection, as measured via VerifyNow[®].

The primary PD variable (PRU_{30m}) is the platelet reactivity as measured by VerifyNow[®] at 30 min after study drug injection [see the table of assessments in the protocol, table 2].

The analysis variable of the PD response is defined as follows for a given subject:

$$\begin{aligned} & \text{IF } PRU_{30m} < 100 \\ & \text{THEN } PD \text{ response} = \text{YES} \\ & \text{ELSE } PD \text{ response} = \text{NO} \end{aligned}$$

PRU time is based on planned time point and not on the actual collection time.

Supportive primary PD endpoint

The following endpoint is not described in the protocol and has been added. The main purpose is to assess the effect of the two study treatment doses, when relaxing the time of a PRU < 100, i.e., considering as a response a PRU < 100 at 15, 30 or 60 min. post injection.

This endpoint is defined as per the following algorithm and will describe the subject's *PD response within the 1st hour*:

*IF minimum of (PRU_{15m}, PRU_{30m}, PRU_{60m}) < 100
THEN PD response within 1st hour = YES
ELSE PD response within 1st hour = NO*

Where PRU_{15m}, PRU_{30m}, and PRU_{60m} refer to PRU measured by VerifyNow® at 15, 30, and 60 minutes after study drug administration.

PRU time is based on planned time point and not on the actual collection time.

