10 GENERAL DEFINITIONS AND DERIVATIONS

10.1 Analysis periods and visit windows

The treatment period is defined as the period starting from time of study drug administration up to 48 hours post administration. However, some assessments may only have the date reported and no time reported (either the time was not planned to be collected or is missing). In this case it will be assumed that the 48 hours treatment period corresponds to the day of study drug administration and to the two following days (1st, 2nd and 3rd day of the treatment period).

This may result in an over-estimated duration of the treatment period for those events that do not have assessment time.

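### A compliant End-of-Study laboratory draw timed between 48 and 50 h falls outside the treatment-emergent laboratory window and out of the marked-abnormality table

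*SAP*

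**What the plan says.** - **Schedule.** Protocol Table 2 marks laboratory tests at screening and at EOS only, and gives EOS as 48 h with a tolerance of 2 h on either side.
- **Laboratory rule.** Protocol 10.2.4.3 closes the treatment-emergent interval for marked abnormalities at "48 h after date/time of last study treatment administration". SAP 7.4.1 requires that the sample was "collected at time of study drug administration or within the first 48 hours (2 days) after study administration". Neither states a tolerance.
- **Treatment period.** In protocol 3.1.1 it "Starts with subject's randomization and ends after the End-of-Study (EOS) assessments". SAP 2.3 and SAP 10.1 end it 48 h after dosing.
- **Samples without a time.** For these, SAP 10.1 says that "it will be assumed that the 48 hours treatment period corresponds to the day of study drug administration and to the two following days".
- **Planned time points.** For platelet reactivity, SAP 6.8.1.1 states that "PRU time is based on planned time point and not on the actual collection time". There is no matching rule for laboratory samples.
- **Recording of times.** For PK samples, protocol 7.2.3.1.1 says: "The date and exact actual clock time of collection of each blood sample will be entered in the eCRF". Protocol 7.2.3.2.1 asks the same for PD samples. For safety laboratory samples the protocol text gives no such instruction; protocol 7.2.5.1 refers to the laboratory manual for collection details.

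**The concern.** Treatment-emergent marked laboratory abnormalities are a named safety endpoint (protocol 6.3) with a planned table (protocol 10.3.5.2, SAP 7.4.1 and 7.4.2). The EOS draw is the only scheduled post-dose sample that can supply that table. The cut-off sits exactly at the nominal time of that draw, so a delay of a few minutes, well within the schedule, is enough to remove a result. Case counts in the table can only fall.

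A second output may be affected. Protocol 10.3.5.2 also plans the change from baseline to the last value in the treatment period. Under the protocol's own treatment period a late EOS value belongs in that summary. Under the SAP's 48 h period it could be left out.

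**Working it through.** The plan states no figure of its own on this point, so there is nothing to reproduce. The check compares two intervals.

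**Inputs from the documents**
- Compliant EOS draw: 48 − 2 = 46 h to 48 + 2 = 50 h (protocol Table 2).
- Treatment-emergent interval for timed samples: 0 to 48 h (protocol 10.2.4.3, SAP 7.4.1).
- Planned size: 21 evaluable subjects per arm (protocol 10.5).

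**Step 1: overlap.** Compliant hours counted: 48 − 46 = 2. Compliant hours not counted: 50 − 48 = 2. Share of the window outside the rule: 2/4. A draw at exactly 48 h is counted. This is the only size that comes from the documents alone.

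**Step 2: can another rule bring the late draw back?** The mention of 2 days in SAP 7.4.1 could be read as calendar days. But protocol 10.2.4.3 works with date and time, and SAP 10.1 reserves the calendar-day reading for assessments without a time. For timed samples the limit in hours therefore governs. Assignment by planned time point is written for platelet reactivity only.

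**Step 3: samples with a date only.** A draw at 48 + x h falls after the second following day only if dosing took place within x h of midnight; for a 50 h draw, at 22:00 or later. Assume that dosing is spread evenly over 24 h. Then a 50 h draw is kept with probability 1 − 2/24 = 91.7%. With x also even over 0 to 2 h, the mean of x is 1 h and the share kept is 1 − 1/24 = 95.8%. The loss therefore arises almost entirely when times are recorded.

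**Step 4: illustration for timed samples.** Let s be the share of EOS draws later than 48 h. The documents give no draw times, so every value of s is an assumption. Samples excluded per arm = 21 × s. There are two possible effects on the reported rate:
- If all at-risk subjects stay in the denominator (a reading of SAP 7.4.2), reported rate / true rate = 1 − s.
- If subjects without a qualifying sample are treated as missing and removed (SAP 8.1.2), there is no expected bias, provided draw time is unrelated to outcome, and the standard error rises by 1/√(1 − s).

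| s (assumed) | Excluded of 21 | Reported / true rate, at-risk denominator | Standard error factor, missing removed |
|---|---|---|---|
| 0.25 | 5.25 | 0.75 | 1.15 |
| 0.50 (symmetric around 48 h) | 10.5 | 0.50 | 1.41 |
| 0.75 | 15.75 | 0.25 | 2.00 |

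The range could be wider. Normal draw times truncated to 46 to 50 h, with mean 47 to 49 h and SD 0.5 to 1 h, give s from 2% to 98%. An unscheduled central laboratory sample taken by 48 h would reduce the loss for that subject.

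**The case against.** **The 48 h limit may be deliberate.** SAP 2.3 and 10.1 use it for the treatment period, and SAP 10.1 describes the wider date-only period as an over-estimate. Protocol 9.1.4 justifies 48 h for adverse events as covering at least five half-lives; with the longest half-life in protocol 1.2.2.3, 5 × 9.2 = 46 h. One exposure window for adverse events and laboratory data is defensible. A reader might infer that the missing tolerance is plainly a drafting slip, but the documents do not support that. What stands against the limit is narrower: whatever its purpose, it does not fit the one scheduled laboratory draw or the protocol's treatment period.

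**The loss is not known.** A reader might infer that half of the EOS samples will disappear. The documents do not support that either. They give no draw times, do not expressly order clock times for safety samples, and leave the denominator open: SAP 7.4.2 defines at-risk subjects by pre-dose status only, while SAP 8.1.2 removes missing values unless the table shells say otherwise. This objection stands and limits the claim to two of four compliant hours.

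**The data are not lost to the report.** This is largely right. Late values stay in the by-visit summaries and in the listings, including the listing of marked abnormalities (SAP 7.4.2), and "the presentation of the safety data will be purely descriptive" (protocol 3.2). Protocol 7.2.5.1 also requires clinically relevant abnormalities to be reported as adverse events, but that is only a partial safeguard. An abnormality first seen in a late draw, with its onset recorded after 48 h, is not treatment-emergent under protocol 10.2.4.1 and SAP 7.2.1.2. It would be listed but would not appear in the treatment-emergent tables of SAP 7.2.2.

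**Conclusion.** The mismatch holds and is minor. Where sample times are recorded, the plan as written leaves compliant EOS laboratory draws between 48 and 50 h out of the treatment-emergent marked-abnormality table. The size supported by the documents is two of the four compliant hours. The share of samples is unknown; one half applies only if draws are symmetric around 48 h. If only dates are recorded, almost nothing is lost. The consequence is either an understated percentage or reduced precision, and the SAP does not settle which. The primary result is unaffected.

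The comparison of intervals is certain. The practical effect is less so, because it depends on whether clock times are captured for safety samples and on the laboratory manual and table shells, which are not part of the documents reviewed.

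**What to change.** 1. In SAP 7.4.1, count the EOS laboratory sample as treatment-emergent when it is drawn within the protocol window, that is up to 50 h. Alternatively, assign it by planned time point, as SAP 6.8.1.1 does for platelet reactivity, provided that it was drawn within that window. Samples taken after 50 h stay out of this table and remain in the listings.
2. Apply the same rule to any laboratory summary of the last value in the treatment period.
3. Record the change from protocol 10.2.4.3 in SAP section 11.
4. Leave the 48 h definition for treatment-emergent adverse events unchanged, and footnote the laboratory table to say that its window is 2 h longer.

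The cost is a sentence in SAP 7.4.1, its extension to the last-value summary, one entry in section 11 and one footnote. It needs no new data and changes neither procedures nor adverse event definitions. The price is a 2 h difference between the laboratory and adverse event windows, which the footnote discloses.

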7.4.2 Analysis

Descriptive summary statistics by visit and study treatment group will be provided for observed values and, when reported at baseline and post-baseline, absolute changes from baseline by category (hematology/coagulation, chemistry) and by parameter. Data will be displayed in SI units as provided by the central laboratory.

Treatment-emergent laboratory abnormalities will be summarized by laboratory category, variable and severity (marked laboratory abnormality).

Only subjects at risk, i.e., with no marked abnormality present prior to study drug start, will be included in these analyses.

For each laboratory category, a listing of the value at each time point, in SI units, for all variables and the changes from baseline (continuous and categorical), as well as the abnormality grade/flag will be produced and will include all visits. The values not considered in the analyses, i.e., local laboratories, will be flagged. A listing of subjects with at least 1 marked laboratory abnormality will also be provided.

7.5 Electrocardiography analysis

Not applicable.

7.6 Vital signs and body weight

7.6.1 Blood pressure and pulse rate analysis

This includes the systolic and diastolic blood pressures (sitting and/or supine), and pulse rate.

Systolic and diastolic blood pressures will be summarized regardless of the subject position at time of measure.

A listing of values, in SI units, for all variables and the changes from baseline (continuous and categorical) as well as the abnormality grade/flag will be produced and includes all time points. The values not included in the analyses will be flagged.

For each parameter at each time point over the course of the study, quantitative descriptive statistics for the value and the change from baseline will be presented by parameter, by time point and treatment group.

7.6.2 Body weight, and other vital sign analyses

Body weight values and assessment date will be listed.

7.7 Other safety variables and analyses

Not applicable.

8 GENERAL STATISTICAL METHODOLOGY

Data will be analyzed using SAS version 9.4 or higher.

8.1 General rules for data presentations

General rules for data presentations as described below are followed unless otherwise specified.

Data are listed and summarized by descriptive statistics (tables or figures) as described below.

8.1.1 Treatment groups

The study included the following 2 groups corresponding to the 2 study treatment groups (i.e., ACT-246475 8 mg and ACT-246475 16 mg). All analyses, unless stated otherwise, will be reported by those 2 treatment arms, and overall, in this order.

8.1.2 Descriptive statistics

Descriptive statistics will be provided by dose group and overall, depending on the nature of the criteria:

Quantitative:

Number of observed values, mean, SD, minimum and maximum, median, 1st and 3rd quartiles.

Qualitative:

Number of observed values, number of missing values, number and percentage of subjects per level/category.

Unless otherwise specified in the table shells, the percentage calculation will not consider missing values in denominators.

The number of missing values is displayed only if > 0 . For categorical variables, those missing are displayed after the last category and no percentage is reported.

Listings are grouped by dose group (same order as in tables headers, if applicable, screening failures are listed last).

Raw data listings, if required, are based on datasets as received. All data collected are displayed, including unscheduled visits (if any).

8.2 Efficacy analyses

Not applicable.

9 INTERIM ANALYSES

Not applicable.

10 GENERAL DEFINITIONS AND DERIVATIONS

10.1 Analysis periods and visit windows

The treatment period is defined as the period starting from time of study drug administration up to 48 hours post administration. However, some assessments may only have the date reported and no time reported (either the time was not planned to be collected or is missing). In this case it will be assumed that the 48 hours treatment period corresponds to the day of study drug administration and to the two following days (1st, 2nd and 3rd day of the treatment period).

This may result in an over-estimated duration of the treatment period for those events that do not have assessment time.

10.2 Dates, times and days

10.2.1 Definition of study start

Study start day is the day of informed consent signature.

10.2.2 Baseline

Baseline is the last non-missing assessment performed or value measured before or on the day and time of study drug administration (i.e., prior to study treatment administration), unless otherwise defined in the specific analysis section.

Subjects without any data for a parameter before treatment administration will have a missing baseline (and therefore a missing change from baseline) value for this parameter.

If it is not possible to allocate an event/measure to the baseline period (missing date and/or time), it will be considered as being post-baseline.

